We will determine the degree to which health literacy moderates the relationship between depression and associated constructs of rumination, pain intensity, pain interference, sleep disturbance, and fatigue. Depression will be measured using both the Patient Health Questionnaire (PHQ-9), a nine-item scale with each item scored between 0 and 3 providing a 0-27 severity score with higher scores representing greater depression severity. The NIH Patient-Reported Outcomes Measurement Information System (PROMIS Profile 57 v 2.0) will also be used to measure depression, as well as pain intensity, pain interference, sleep disturbance, and fatigue. PROMIS is a self-report measure with subscales producing a T-Score; higher T-scores representing a higher level of the construct. Rumination will be measured using the Ruminative Responses Scale (RRS) short form, a 10-item form that measures two factors, brooding and reflection. The RRS uses a four-point scale for each item with a total score derived from the sum of the individual items. Higher scores indicate higher levels of rumination. All variables will be examined in a continuous manner, rather than using cut scores.

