Multiple regression analyses will be conducted using the *lm()* function in base R to test a moderation model for the PHQ-9 and PROMIS depression scale separately with health literacy (a continuous score from Health LiTT) acting as the proposed moderator between depression symptoms and pain intensity and interference, sleep disturbance, fatigue, and rumination. PROMIS profile scale scores will be entered into the regression model together. Health literacy will then be added as a moderator. In accord with our hypotheses, the addition of health literacy into the model should explain a significantly greater portion of the variance than symptom scores alone. PROMIS profile scale scores will then be removed from the model in a step-down procedure to determine the contribution of each scale to the model. We hypothesize that there will be a significant interaction between health literacy and symptoms scores. Specifically, we hypothesize that having higher health literacy will result in a stronger association between rumination and depression, whereas individuals with lower health literacy will evidence a stronger association between somatic symptoms (pain, fatigue, and sleep disturbance) and depression. Additionally, we predict that there will be a greater effect of health literacy for analyses involving the PHQ-9 than the PROMIS. We will also compare standardized beta coefficients to determine the strength of the effect for each variable. As we anticipate few instances of missing data due to our computerized administration, listwise deletion will be used in the presence of missing data.

Meaning and Purpose Analyses

DIF Analysis. In addition to the lordif approach described above, we will conduct DIF analysis using the moderated nonlinear factor analysis (MNLFA) approach, which allows health literacy to be continuous, rather than categorical (high versus low). Our analyses will examine the impact of health literacy on DIF as well as possible moderation by administration type (pencil-and-paper versus talking touchscreen). The MNLFA enables the examination of both variables simultaneously. Our a priori hypothesis is that DIF will be observed across levels of health literacy for paper-and-pencil based testing. We further hypothesize that DIF will also be found for the talking touchscreen, but for fewer items. Mplus permits IRT analyses with constraints imposed such that each item slope is linearly related to external variables – in our case, this would be:

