Hypothesis 1: Depression predicts pain at 6-month follow-up, mediated by sleep disturbance at 3-month follow-up: We hypothesize depression will be related to *more* sleep problems at 3-month follow up, which in turn will lead to *more* pain at 6-months. Depression at baseline will be operationalized by the PROMIS depression scale within the 57-item Profile. Note that we made an *a priori* decision to use PROMIS rather than the PHQ-9 for depression because the PHQ-9 contains questions about sleep whereas the PROMIS depression scale does not. We will assess sleep at 3-month follow-up using the PROMIS sleep disturbance subscale of the 57-item Profile. We will use two different PROMIS Profile scales to assess pain at 6-month follow-up: pain intensity and pain interference. These hypotheses were formulated before any data were examined.

To carry out these analyses, we will use the *mediate* package in R for these analyses. The form of the mediation is depression at baseline → worse sleep at 3mo → more pain at 6mo. We will first create the regression models for depression predicting sleep, and sleep predicting pain. Sleep as a mediator will be tested in the *mediate* package based on the 95% bca confidence intervals.

Hypothesis 2: Pain predicts depression at 6-month follow-up, mediated by sleep disturbance at 3-month follow-up: To examine bidirectional causality, we will analyze the mediation from Hypothesis 1 in the opposite direction, specifically Pain at baseline → worse sleep at 3mo → more depression at 6mo. The same mediation procedures will be used, as in Hypothesis 1, with two different pain measures as the initial covariate: pain intensity and pain interference.

Hypothesis 3: Sex will moderate mediation relationships found in Hypotheses 1 & 2. Given that depression disproportionately affects females when compared to males, we plan to conduct moderated

mediation for sex. We hypothesize sex will moderate the mediation, with female sex being associated with stronger associations among depression and sleep, and sleep and pain.

Exploratory analyses. We anticipate that age influences depression, sleep, pain, but have no directional hypothesis for age. Thus, age will be included as an exploratory variable in the above-mentioned mediations.

Statistical Analysis Plan Addendum: Vaccine Confidence Analysis from phone-based substudy (section added 10 March 2021)

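### The SAP avoids the PHQ-9 in the sleep mediation analysis because of sleep content, yet regresses the full PHQ-9 on PROMIS sleep disturbance in the moderation models without addressing the overlap

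*SAP*

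**What the plan says.** Two current sections of the SAP treat the same overlap differently.

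- **Sleep as a mediator between depression and chronic pain, Hypothesis 1.** The SAP records an a priori choice of PROMIS depression over the PHQ-9, on the ground that "the PHQ-9 contains questions about sleep whereas the PROMIS depression scale does not".
- **Prediction of depression: Health literacy as a moderator.** The PHQ-9 is described as "a nine-item scale with each item scored between 0 and 3 providing a 0-27 severity score", with nothing removed. The PROMIS Profile "will also be used to measure depression, as well as pain intensity, pain interference, sleep disturbance, and fatigue". Regressions are planned "to test a moderation model for the PHQ-9 and PROMIS depression scale separately with health literacy" as the moderator of the relation "between depression symptoms and pain intensity and interference, sleep disturbance, fatigue, and rumination".

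Four outputs are planned in the second section:

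- the symptom by literacy terms: "We hypothesize that there will be a significant interaction between health literacy and symptoms scores";
- a step-down removal of the PROMIS scales, to see what each contributes;
- a comparison of standardized betas across predictors;
- a contrast between the two depression scales: "we predict that there will be a greater effect of health literacy for analyses involving the PHQ-9 than the PROMIS".

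The section does not mention the sleep overlap, a PHQ-9 score without sleep content, or a reason why the overlap is acceptable there.

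**The concern.** When an outcome contains questions on the same subject as a predictor, part of their association is the subject correlated with itself. The SAP accepts this for the mediation analysis, where depression and sleep are measured at visits three months apart. The moderation section states no lag between outcome and predictors, so the protection is missing where the overlap may matter at least as much.

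Two things are at stake directly. Sleep disturbance may look like a stronger correlate of depression than it is, which affects the beta ranking and the step-down. A difference between the PHQ-9 and PROMIS models may be read as a literacy finding when the two scales also differ in sleep content. The interaction test is at risk only under a further condition, set out below.

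**Working it through.** **The plan's own figure.** The section states no sample size, power or effect size. Its only arithmetic is the PHQ-9 range, 9 items x 3 = 27, which is correct. The size of the overlap effect therefore has to be illustrated by simulation.

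**Inputs from the documents.** Loading 0.7 (borrowed from the SAP's power simulation, which had another purpose); two-sided alpha 0.05 (SAP, Overview); N = 728 (SAP, Study Objectives). The moderation section gives no N, and 728 is an upper value because some participants lack questionnaires and listwise deletion is planned.

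**Assumptions.** One or two PHQ-9 items concern sleep (the SAP gives no count). Those items also load directly on sleep with w = 0.20 or 0.35. Depression correlates rho = 0.4, 0.5 or 0.6 with each symptom, and the symptoms correlate 0.4 with one another. Items have four categories. Literacy is continuous and unrelated to the symptoms. There is no true interaction. A single pain predictor stands in for the SAP's two.

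**Model.** Latent item = 0.7 x depression + w x sleep + error, with w = 0 for the other items. The full score sums nine items; the sleep-free score omits the sleep item(s). Each standardized score is regressed on sleep, fatigue, pain, rumination, literacy and the four products with literacy.

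**Step 1: sleep beta (400,000 simulated participants per run).**

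| rho | sleep items | w | full | sleep-free | difference |
|---|---|---|---|---|---|
| 0.4 | 1 | 0.20 | 0.178 | 0.158 | 0.020 |
| 0.4 | 1 | 0.35 | 0.201 | 0.155 | 0.046 |
| 0.4 | 2 | 0.20 | 0.206 | 0.153 | 0.053 |
| 0.4 | 2 | 0.35 | 0.242 | 0.155 | 0.087 |
| 0.5 | 1 | 0.20 | 0.223 | 0.194 | 0.029 |
| 0.5 | 1 | 0.35 | 0.238 | 0.196 | 0.042 |
| 0.5 | 2 | 0.20 | 0.247 | 0.193 | 0.054 |
| 0.5 | 2 | 0.35 | 0.278 | 0.193 | 0.085 |
| 0.6 | 1 | 0.20 | 0.258 | 0.232 | 0.026 |
| 0.6 | 1 | 0.35 | 0.276 | 0.235 | 0.041 |
| 0.6 | 2 | 0.20 | 0.280 | 0.230 | 0.050 |
| 0.6 | 2 | 0.35 | 0.314 | 0.229 | 0.085 |

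**Step 2: ranking.** The simulated symptoms are equally related to depression, so their betas should be equal. At rho = 0.5, one item, w = 0.35, the sleep-free betas are 0.196 (sleep), 0.195 (fatigue) and 0.196 (pain). With the full score they are 0.238, 0.192 and 0.192, so overlap alone puts sleep ahead. Unique variance goes with the squared beta: (0.238/0.196)² = 1.47 for one item and (0.278/0.193)² = 2.07 for two, both at the larger w.

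**Step 3: sleep by literacy interaction (coefficients at rho = 0.5 from 400,000 participants; rejection rates from 2,000 replicates at N = 728).** The Monte Carlo standard error at 5% is √(0.05 x 0.95 / 2000), about 0.5 percentage points.

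| w at low / high literacy | sleep items | coefficient | rejection rate |
|---|---|---|---|
| 0.35 / 0.35 | 1 | -0.0006 | 4.9% |
| 0.35 / 0.35 | 2 | -0.0002 | 5.1% |
| 0.35 / 0.10 | 1 | -0.0115 | 7.0% |
| 0.35 / 0.10 | 2 | -0.0269 | 12.1% |
| 0.10 / 0.35 | 1 | +0.0161 | not run |
| 0.10 / 0.35 | 2 | +0.0256 | not run |

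A negative coefficient means a stronger sleep association at low literacy, which is the SAP's prediction. The reverse pattern gives a bias of similar size against it.

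**Step 4: PHQ-9 versus PROMIS.** By the SAP's own statement the scales differ in sleep content. An observed difference in the literacy effect therefore has at least two explanations, and the planned models contain nothing to separate them. Equal overlap would not by itself create a difference in the interaction, but the plan has no step to show that the overlap is equal.

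**The case against.** The best defence has four parts.

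- **PROMIS depression is modelled in parallel.** By the SAP's account it has no sleep questions, so the sleep term can be checked on a clean outcome. This stands for the sleep term. It does not rescue the scale contrast, because PROMIS is one side of that comparison.
- **Item behaviour by literacy is already studied.** The PHQ-9 is among the scales tested for differential item functioning. That would help to reveal a sleep item that behaves differently by literacy, but the results are not linked to the moderation models.
- **The intact PHQ-9 is a legitimate outcome.** The study asks how literacy affects questionnaires as they are used, and the PHQ-9 was set aside for the mediation analysis only. This stands: a reader might infer that the SAP rejects the PHQ-9 in general, and it does not. The full score should stay.
- **The interaction is largely safe.** This stands when overlap is equal across literacy. The SAP also predicts lower item slopes at low literacy, which could push the bias against its own hypothesis. That prediction concerns items and their own trait, however, and does not fix the direction for a sleep item's link to sleep.

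A reader might also infer that all the somatic associations are inflated. The documents establish overlap for sleep only. In the simulation the fatigue and pain betas moved by about 0.01 or less and were, if anything, slightly lower with overlap.

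**Conclusion.** The inconsistency is real and lies in current text. With the full PHQ-9, shared content inflates the sleep association, by about 0.02 to 0.05 in standardized beta for one sleep item and 0.05 to 0.09 for two. That is enough to change the order of predictors of similar strength. The PHQ-9 versus PROMIS prediction cannot be interpreted as a literacy effect while the difference in sleep content is left in.

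A reader might go further and conclude that the interaction test has an inflated error rate. That does not follow from overlap alone. It needs overlap that varies with literacy, which the documents make plausible but do not establish. Under the assumed contrast of 0.35 against 0.10 the rate is about 7% to 12%; it was calculated only for stronger overlap at low literacy.

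Apart from the borrowed 0.7 loading, the alpha and N = 728, every simulation input is an assumption. The sizes show the order of magnitude and are not estimates for this study. The point is a cheap improvement to interpretation and does not invalidate the analysis.

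**What to change.** In the SAP section on predicting depression, add that each PHQ-9 moderation model will also be run with the PHQ-9 scored without its sleep content, and that this will be reported beside the full 0-27 score. Name the omitted item(s) from the instrument. State that conclusions on the sleep term, the standardized-beta ranking and the PHQ-9 versus PROMIS contrast will rest on results that hold with the sleep-free score. Add a sentence explaining why the full PHQ-9 is kept here although it was set aside for the mediation analysis. Leave fatigue-related items in unless the sponsor confirms from the items that they overlap with the fatigue predictor.

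The version notes under Cognitive Correlates of Rumination say that some analyses from this section had already been carried out. The addition should therefore be dated and recorded as a change with its reason, as the SAP's Overview requires for changed methods, and should not be presented as fixed in advance for results already seen.

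The cost is a few sentences, one re-scored outcome and a second set of models, with no new data. The drawback is an extra score that is not the standard PHQ-9 total and cannot be read on the 0-27 severity scale.

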- 4.1 Research setting: Participants will be recruited from clinics within Northwestern Medicine, or will be invited to come to our clinical research space on campus for three visits: Baseline, 3-month follow-up, and 6-month follow-up. Participants actively enrolled in the study during the COVID-19 pandemic will have extended time-frames to complete the 3-month follow-up and 6-month follow-up visit. Participants will come in for their 3-month follow-up visit when it is feasible and reasonably safe for them to do so and then will aim to complete their 6-month follow-up visit 3 months after their second visit. While participants are enrolled in the phone-based protocol, any outstanding in-person visits will be put on hold until the completion of the phone-based protocol.
- 4.2 Study design and rationale: The study is a two-group, three time-point experimental design. The two study groups are paper-and-pencil questionnaires versus a computerized talking touchscreen interface. The three time points are baseline, 3-month follow-up, and 6-month follow-up. The rationale for this design is that it will allow us to compare two models of administration as well as to examine how the psychometric properties of questionnaires change over time.

As a result of the COVID-19 pandemic, the study will add phone-based assessments to the study design. These study phone visits will be in addition to the original three time-points of the study design. The phone-based study visits will also happen at three time-points (baseline, 3-month follow-up, and 6-month follow-up). This design will allow us to examine the properties of the questionnaires that change over time as well as compare the phone-based assessments to the in-person assessments (via paper-and-pencil or talking touchscreen interface) that participants completed before the COVID-19 pandemic and, possibly, after the COVID-19 pandemic.

4.3 Description of research procedures and activities:

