Using a large sample, we will determine the psychometric properties of health questionnaires across levels of health literacy. Testing will be conducted in English and Spanish, across two modes of administration (paper-and-pencil vs. talking touchscreen). Each participant will have three visits (baseline, 3-month, and 6-month follow-up), described below, in order to determine changes in psychometric properties over time. We will use *differential item functioning* (DIF) and other psychometric analyses to identify questionnaire items with varying characteristics across levels of health literacy. Before the COVID-19 pandemic, our original plan was to recruit $N = 1216$ participants for in-person assessments. At the time of this plan our final N is 728 participants who have completed a health literacy assessment; some of these participants are missing data on subsequent questionnaires. In-person recruitment was put on hold during the COVID-19 pandemic; in order to adapt the the pandemic, a subset of participants ($N = 304$) was invited to a phone-based protocol that included data collection about the impact of COVID-19, vaccine confidence, and health-related quality-of-life (PROMIS-29 profile).

- **Develop alternative modes of test administration that can better accommodate people with low health literacy.** National statistics indicate that 14% of adults in the United States have below basic reading skills, and over 75 million Americans have below basic or basic health literacy skills.¹⁴ These data strongly indicate that many individuals seeking health care will have difficulties with written questionnaires, even those that have been carefully developed such as those in the NIH PROMIS. We will test an alternative mode of administration that has been specifically designed to aid people of low health literacy – a computer-assisted “talking” version that uses speech technology that participants can privately access as needed to have items and response options

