Short Portable Mental Status Questionnaire (SPMSQ)	To determine cognitive status to ensure the possible participant has sufficient mental status to participate
Demographics	To assess participant characteristics
Health Literacy Assessment (Health LiTT)	Assessment of health literacy.
NUMI	Assessment of numeracy. That is, how well the person can process numerical information
PROMIS Profile	To assess health-related quality of life.
PHQ-9	Self-report measure of depression.
Berlin Questionnaire (for sleep)	Self-report measure of sleep quality
Purpose and Meaning (NIH Toolbox)	Self-report measure of the degree of meaning and purpose a person feels in their life.
Ruminative Responses Scale (RRS)	Self-report measure of negative, repetitive thoughts
PTSD Checklist	Self-report measure of posttraumatic stress disorder symptoms
* C-SSRS Lifetime	Self-report measure of recent history of suicidal ideation and behavior. (This is not a variable of interest that will be used only to ensure patients' safety).
*C-SSRS Last Contact	Self-report measure of suicidal ideation and behavior since the individual's most recent assessment. (Used only as necessary to ensure patients' safety).
Visit 1, but if missing at Visit 1, then given at Visit 2 or 3	
Screening tools for Alzheimer's disease and related dementias (ADRD)	This brief battery contains the Montreal Cognitive Assessment-Basic (MOCA-B), and selected items from the RUDAS. * Note: These items were added to the study after recruitment began, so we give them at Visit 1, but if they were not given at Visit 1, they are then administered at Visit 2 or 3
Visit 2 (3-months)	
PROMIS Profile	To assess health-related quality of life
PHQ-9	Self-report measure of depression
Berlin Questionnaire (for sleep)	Self-report measure of sleep quality
Purpose and Meaning (NIH Toolbox)	Self-report measure of the degree of meaning and purpose a person feels in their life.
RRS	Self-report measure of negative, repetitive thoughts.
PTSD Checklist	Self-report measure of posttraumatic stress disorder symptoms.
*C-SSRS Lifetime	Self-report measure of recent history of suicidal ideation and behavior. (This is not a variable of interest that will be used only to ensure patients' safety).
*C-SSRS Last Contact	Self-report measure of suicidal ideation and behavior since the individual's most recent assessment. (Used only as necessary to ensure patients' safety).
Visit 3 (6-months)	

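### The sleep-mediation outline names no baseline sleep or baseline outcome covariate, so it can find mediation in both directions when no symptom affects another over time

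*SAP*

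**What the plan says.** The plan is in the SAP section on sleep as a mediator between depression and chronic pain, restricted to participants tested in English.

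- **Hypothesis 1:** "Depression predicts pain at 6-month follow-up, mediated by sleep disturbance at 3-month follow-up". Its models are described in one sentence: "We will first create the regression models for depression predicting sleep, and sleep predicting pain". The indirect effect is judged by a 95% BCa bootstrap interval.
- **Hypothesis 2:** "To examine bidirectional causality, we will analyze the mediation from Hypothesis 1 in the opposite direction". It runs from baseline pain through 3-month sleep to 6-month depression, by the same procedures.
- **Other variables:** sex is a moderator (Hypothesis 3), and "age will be included as an exploratory variable in the above-mentioned mediations". No other covariate is named here, and no other section adds one to this analysis.
- **Safeguards present:** the three measures are ordered in time, and PROMIS depression is preferred "because the PHQ-9 contains questions about sleep whereas the PROMIS depression scale does not".
- **Data available:** SAP Table 1 lists the PROMIS Profile at Visits 1, 2 and 3, so baseline depression, sleep and pain scores are all collected.
- **Sample size:** none is given for this analysis. The Meaning and Purpose section reports 566 English speakers at baseline through March 2020, the only achieved English count. SAP Table 2 planned 304 English speakers per site, 608 in all. The number with three visits is not stated. Study Objectives notes that "some of these participants are missing data on subsequent questionnaires", and Protocol 4.1 says that participants enrolled during the pandemic "will have extended time-frames to complete the 3-month follow-up and 6-month follow-up visit".

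**The concern.** Symptom scores taken three months apart usually resemble each other, and people who score high on one symptom often score high on others. Baseline depression can then predict 3-month sleep only because it goes with baseline sleep, which persists. Likewise 3-month sleep can predict 6-month pain only because the two were already associated. The product of the two paths is then non-zero although neither is an effect over time.

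The reversed chain has the same weakness, so agreement between the two directions is not reassurance: both can be significant for the same reason. At stake is a report of causality in both directions that reflects only correlated starting levels. Time order and the avoidance of overlapping sleep items do not deal with this.

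**Working it through.** The plan states no error rate, power or sample size here, so there is no figure to reproduce. All inputs below are assumptions.

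**Inputs.** r = correlation between any two symptoms at baseline (.2 or .4). s = correlation of a scale with itself one visit later (.5–.7). n with all three visits = 200 or 400, which is 200/566 = 35% and 400/566 = 71% of the achieved English count. No symptom affects another. The exposure is kept in the outcome model, the reading more favourable to the plan.

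**Population paths, unadjusted** (standardised scales). With a = corr(X,M),
b = [corr(Y,M) − corr(Y,X)·corr(M,X)] / [1 − corr(M,X)²]. Take r=.4, s=.6.

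- *Shared later shocks.* a = rs = .24. b = rs(1−rs²)/(1−r²s²) = .24×.856/.9424 = .218. Product .052.
- *Independent later shocks.* a = .24. b = rs³(1−r)/(1−r²s²) = .4×.216×.6/.9424 = .055. Product .013.
- *Stable traits with independent occasion noise.* a = r = .40. b = r/(1+r) = .4/1.4 = .286. Product .114. Holding the observed correlation at .4 requires trait correlations of r/s, from .4/.7 = .57 to .4/.5 = .80.

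The true effect over time is zero in each case. At n=400 the standard error of b is at most about √(1/(400×.9424)) = .0515. So b is about .218/.0515 = 4.2 standard errors from zero with shared shocks, but .055/.0515 = 1.1 with independent shocks.

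**Simulated rate at which both directions are falsely significant in the same sample** (500–1,000 data sets per cell, 95% Monte Carlo interval for a×b, s = .5–.7):

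| Later structure | r=.2, n=200 | r=.4, n=200 | r=.4, n=400 |
|---|---|---|---|
| Independent shocks | 0–1% | 0–5% | 1–19% |
| Shared shocks | 1–8% | 40–84% | 88–100% |
| Stable traits, independent noise | 30–35% | 97–100% | 97–100% |

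With shared shocks at r=.2, n=400, the rate is about 9–38%. Simulation error moves the ends of these ranges by a few points.

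**Checks.**
- If the exposure is left out of the outcome model, as the SAP sentence literally reads, independent shocks at r=.4, n=400 give 3–63%.
- With the planned BCa interval at s=.6, shared shocks at r=.4 give 74% (n=200) and 98% (n=400). Independent shocks at n=400 give 5%.
- A BCa control at n=300 with zero correlations gives 0%, so the method itself is not at fault.

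**After adding the baselines.** Under either shock structure, 3-month sleep equals s × baseline sleep plus a shock. The coefficient on baseline depression is therefore zero, and so is the product. Per-direction false rates fall to 0–0.6% (independent) and about 0.3–6% (shared; 7–9% with BCa at r=.4, n=400, s=.6). Under stable traits the coefficient stays positive: at r=.4, s=.6 it is [.4 − .4×(.4+.6+.4)/1.8]/.6 = .148. The per-direction false rate is then about 20–77% at r=.4, n=400, and about 1–3% at r=.2, n=200.

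**What the data can show.** From r=.4 at baseline, independent shocks imply between-symptom correlations of rs² = .10–.20 at 3 months and rs⁴ = .03–.10 at 6 months. Under the other two structures they stay at .4.

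**The case against.** - **Silence is not exclusion.** A reader might infer that the SAP rules out baseline adjustment. It does not. The text is a sketch, and does not say whether the exposure stays in the outcome model. But the SAP presents itself as fixing decisions in advance, and it names covariates for its vaccine-confidence and trauma mediation models. Here the decisive covariates are left open.
- **The size is assumed.** A reader might infer that false mediation is the expected result. The documents give no correlations, stability, shock structure or three-visit count, and the illustration runs from 0 to 100%. The highest figures come from the stable-trait case, which needs the strong trait correlations shown above. Only the qualitative point is firm.
- **Adjustment changes the question.** With baselines in the model the estimate concerns effects after baseline, and drops any effect of depression already expressed in baseline sleep. This stands. The SAP does not say which is intended, and should.
- **It is a side analysis.** True: it is observational, English-only and first written for a conference. That limits the weight of the point. But a second, final run is planned, and the stated aim is causal, whereas the rumination section of the same SAP disclaims causal inference.

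**Conclusion.** The concern holds as one of unspecified covariates in an analysis with a causal aim. Followed as outlined, Hypotheses 1 and 2 can both be declared significant when no symptom affects another over time. The chance is small if symptoms are weakly correlated or later shocks are independent. It is large if correlations are near .4 and shocks are shared or traits are stable. The documents do not show which applies, but the between-symptom correlations at 3 and 6 months would help to tell.

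Two further readings are not supported. One is that the fault reaches the DIF analyses or the comparison of touchscreen with paper: neither uses these models. The other is that baseline adjustment would make causal wording safe: it would not if scores are noisy measures of stable traits. Nothing is concluded here about Hypothesis 3. The change is worth making but does not threaten the trial's main results.

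**What to change.** For each pain scale under Hypothesis 1, specify:

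- sleep(3m) ~ depression(0) + sleep(0) + pain(0)
- pain(6m) ~ sleep(3m) + depression(0) + sleep(0) + pain(0)

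Use the mirror image for Hypothesis 2, with 6-month depression as the outcome. Keep the BCa interval. Replace the causal aim with associative wording, as in the SAP section on cognitive correlates of rumination. Report between-symptom correlations at each visit and the number with all three visits. State that the estimate concerns effects after baseline, and that adjustment may not remove false mediation from stable traits. A random-intercept cross-lagged model is an optional sensitivity analysis.

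Cost: no new data are needed, since the baseline scales come from the same visit as the exposure. The SAP's own rules require the change to be documented with justification. It should be labelled post hoc if these data have already been analysed; the documents do not show whether they have.

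Fewer results will be significant. At correlation .4 with independent later shocks, adjusted power is about 6–8% (n=200) and 19–24% (n=400) when both paths are .1, and 53–55% and 87–94% when both are .2. Shared shocks give higher power. The outlined models reject more often when a single depression–sleep–pain chain is real (about 44–100% over these settings), but part of that is confounding.
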